6.14 Analysis of Secondary Endpoints

All secondary analyses are based on the ITT population with missing values imputed at week 8 (WK8) using multiple imputation (MI) assuming MAR using SEED=2460650. In case imputed values are below or above the range of the applicable scale, values will be imputed to respectively the minimum or maximum value of the scale. The following SAS code will be used MI.

```
PROC MI DATA=EFF NIMPUTE=100 SEED=2460650 OUT=MIOUT;  
  CLASS TREATMENT;  
  VAR TREATMENT BASELINE WK8(EOS);  
  FCS REG;  
RUN ;
```

6.14.1 Analyses of Key Secondary Endpoints

The analyses of key secondary objectives will be conducted on the following sequentially ordered endpoints for testing: 1) CGI-I, 2) Conners-3, 3) WFIRS-P.

To preserve the overall type I error rate at 0.05 for the key secondary endpoints, a sequential testing procedure will be used. First, only dose or doses that are significantly different from placebo for the primary endpoint will be tested for secondary endpoints. If the primary endpoint analysis does not reject H01 (i.e. the 400 mg is not superior to placebo) or the primary endpoint analysis rejects only

H_{01} , then no multiplicity adjustment is required. Otherwise, multiplicity adjustment will be performed with the following features.

The first of the secondary endpoints (CGI-I) will be used to test each treatment group to placebo using a sequential testing of the null hypotheses H_{01} : No treatment mean difference between SPN-812 ER 400 mg group and placebo group and H_{02} : No treatment mean difference between SPN-812 ER 200 mg group and placebo group will be performed. If H_{01} is not rejected, then H_{02} will not be tested and the conclusion will be that neither dose groups are efficacious. If H_{01} is rejected, then H_{02} will be tested. If H_{02} is rejected, then it will be concluded that both SPN-812 ER 400 mg and SPN-812 ER 200 mg are superior to Placebo. If H_{02} is not rejected, then it will be concluded that **only** SPN-812 ER 400 mg is superior to placebo. Then, the second secondary endpoint (Conners-3) will be tested in the same manner but only using those doses that were retained from the primary and the first secondary endpoint. Finally, the third key secondary endpoint (WFIRS-P) will be tested in the same manner but only using those doses that were retained from the primary, the first key secondary endpoint and the second key secondary endpoint.

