6.12 Multiple Comparisons/Multiplicity

This is a 3-arm parallel group design. To account for the potential Type I error rate inflation due to multiple dose group comparisons to placebo, a sequential testing procedure with a fixed testing method will be used. The details of this multiplicity adjustment are defined in [Sections 6.13.1](#) and [6.14.1](#).

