6.13 Efficacy Analyses

The efficacy analyses will be based on the ITT population and will be performed on ADHD-RS-5 total score, Conners 3-PS composite T score, Conners 3-SRS composite T score, WFIRS-P total score and PSI-4-SF total scores.

All confidence intervals, statistical tests, and resulting p-values will be reported as two-sided and will be assessed at the 5% significance level and interactions at 10%.

With respect to Analysis of Covariance, the Gamma regression will be used on the original scale, if the normality assumption for the standard ANCOVA model is not met based on diagnostic residual plots based on the data before imputation.

Multiplicity will be adjusted for the primary endpoint and key secondary endpoints.

The mean profiles of ADHD-RS-5 total score, Conners 3-PS composite T score, Conners 3-SRS composite T score, WFIRS-P total score, PSI-4-SF score and CGI-I score will be presented graphically by treatment group and scheduled study visit. In addition, plots of the Cumulative Distribution Functions of Change from Baseline in ADHD-RS-5 will be presented (Figures 14.2.1.1 - 14.2.6.2)

For supportive analysis, the absolute value and change from baseline to Week 8 (EOS) of all efficacy variables will be summarized using descriptive statistics by treatment group and visit (Tables 14.2.5.1- 14.2.5.6).

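### The key secondary procedure does not hold its stated overall 5% across doses and endpoints, because 400 mg goes on at full 5% after 200 mg has failed

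*SAP*

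**What the plan says.** Section 6.14.1 states the aim without qualification: "To preserve the overall type I error rate at 0.05 for the key secondary endpoints, a sequential testing procedure will be used". The endpoints are CGI-I, Conners 3 and WFIRS-P, and the analyses are "conducted on the following sequentially ordered endpoints for testing". Only doses that beat placebo on the primary enter. Within an endpoint, 400 mg is tested first, and 200 mg only if 400 mg is rejected. Conners 3 is then "tested in the same manner but only using those doses that were retained from the primary and the first secondary endpoint", and WFIRS-P is tested "only using those doses that were retained from the primary, the first key secondary endpoint and the second key secondary endpoint".

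No alpha is divided anywhere. Section 6.13 says that every test "will be assessed at the 5% significance level", two-sided, and places the primary and the key secondary endpoints together under multiplicity adjustment. Section 6.12 gives the purpose of the procedure: "To account for the potential Type I error rate inflation due to multiple dose group comparisons to placebo".

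If the primary does not reject for 400 mg, or rejects for 400 mg only, section 6.14.1 says "then no multiplicity adjustment is required". The next sentence is: "Otherwise, multiplicity adjustment will be performed with the following features".

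**The concern.** A fixed sequence at full alpha controls the familywise error because testing stops at the first non-rejection. Here it does not stop. When 200 mg fails an endpoint, 400 mg is retained and tested on the next one, again at 5%. The result is two 5% chains, one per dose, linked only by the rule that 200 mg needs 400 mg on the same endpoint. A trial can then make a false 200 mg claim on one endpoint and, separately, a false 400 mg claim on a later one.

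This is a pivotal trial. Claims on the three key secondary endpoints would be reported as protected at an overall 0.05 that the written rules do not guarantee.

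**Working it through.** **Inputs.** Each test is two-sided at 0.05 (section 6.13). Allocation is 1:1:1 (section 3.4.1), so the two dose-placebo statistics on one endpoint share the placebo arm and correlate 0.5. Section 3.5 gives effect size 0.547, 72 per arm analysed and 100 randomized. The correlation ρ between endpoints is not in the SAP; I assume 0, 0.5, 0.7 and 0.9, with cross-dose, cross-endpoint correlation 0.5ρ.

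**The plan's own figures.** Two-sample t-test power at 72 per arm with effect 0.547 is 0.903, and 72/(1 − 0.279) = 99.9, so 100 per arm. Both reproduce. The overall 0.05 does not, as follows.

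**Step 1: where 5% holds (endpoint order kept).**
- Within one dose, or within one endpoint, the tests form an ordinary fixed sequence: 5%.
- If 400 mg is null first, or both doses are first null on the same endpoint, every false claim requires a false 400 mg rejection there: 5%. Simulation gives 5.0% at every ρ.

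**Step 2: where it leaks.** The leak needs 200 mg to be null on an earlier endpoint than 400 mg. Let both doses work on the primary, 400 mg work on CGI-I, 200 mg be null on CGI-I and 400 mg be null on Conners 3, with the true effects large enough to be certain of rejection. Both null hypotheses are then tested at full 5%:

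FWER = 0.05 + 0.05 − P(both rejected), where the two statistics correlate 0.5ρ.

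At ρ = 0 this is 1 − 0.95² = 0.0975. The bound under any dependence is 0.05 + 0.05 = 0.10.

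| ρ | 0 | 0.5 | 0.7 | 0.9 |
|---|---|---|---|---|
| FWER, section 6.14.1 rules | 9.75% | 9.6% | 9.4% | 9.2% |
| FWER, single stop-at-first-failure sequence | 5.0% | 5.0% | 5.0% | 5.0% |

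The same leak one step later (200 mg null on Conners 3, 400 mg null on WFIRS-P) is of the same size. So is the leak from the primary (200 mg null) to CGI-I (400 mg null), if the family includes the primary as section 6.13 says. For the key secondary endpoints alone, that last pattern stays at 5%.

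**Step 3: finite effects.** Replace certain rejection by an effect of 0.547 for every true effect in the first pattern. This is my assumption: section 3.5 gives 0.547 only for 200 mg on the ADHD-RS-IV. The noncentrality is 0.547√(n/2), which is 3.282 at n = 72 and 3.868 at n = 100. At ρ = 0:

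FWER = 0.05p² + 0.95bj

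Here p is the power of one test, b the chance that both doses win the primary, and j the chance that on CGI-I 400 mg is rejected and the null 200 mg is falsely rejected (normal approximation).

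- n = 72: p = 0.907, b = 0.843, j = 0.0392; 0.0411 + 0.0314 = 0.0725.
- n = 100: p = 0.972, b = 0.949, j = 0.0450; 0.0472 + 0.0405 ≈ 0.0878.

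The other correlations are by simulation (at least 1,000,000 draws each):

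| ρ | 0 | 0.5 | 0.7 | 0.9 |
|---|---|---|---|---|
| 100 per arm | 8.8% | 7.9% | 7.1% | 5.9% |
| 72 per arm | 7.3% | 6.4% | 5.6% | 4.7% |
| 100 per arm, 200 mg effect 0.3 on CGI-I | 4.7% | 4.2% | 3.7% | 3.1% |
| 72 per arm, 200 mg effect 0.3 on CGI-I | 4.1% | 3.4% | 2.9% | 2.5% |

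In the last two rows the 200 mg null on CGI-I is gone, so at ρ = 0 only the term 0.05p² remains.

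**Step 4: the branch where only 400 mg wins the primary.** Take 200 mg null on the primary and 400 mg null on all three key secondary endpoints. If the order is kept, the 400 mg error over the three endpoints is 5.0% at every ρ. If the order were dropped, at ρ = 0 it is 0.95 × (1 − 0.95³) + 0.05 × 0.05 = 0.138, falling to 12.0%, 10.4% and 8.0% at ρ = 0.5, 0.7 and 0.9.

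**The case against.** The strongest reply is that the leak needs a particular pattern: 200 mg works on the primary but has exactly no effect on CGI-I, while 400 mg works on CGI-I and has exactly none on Conners 3. A modest residual 200 mg effect on CGI-I brings the rate below 5%, and at 72 per arm with correlation 0.9 the excess disappears even without one. That limits the practical weight and it stands. It does not rescue the claim, because an unqualified overall rate has to hold for any pattern of true and false nulls. A lower dose that loses its effect earlier than a higher dose is also an ordinary dose-response, and section 6.14.1 itself provides for the outcome that only 400 mg is superior.

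A reader might go further and infer from "then no multiplicity adjustment is required" that the plan drops the endpoint order when only 400 mg wins the primary, so that 400 mg runs at up to 13.8%. The documents do not support that as a finding. The opening sentence of section 6.14.1 orders the endpoints without exception, and section 6.12 ties the adjustment to dose comparisons. With one dose left, the sentence most naturally means that no dose adjustment is needed. The word that opens "Otherwise, multiplicity adjustment will be performed with the following features" leaves the other reading open, so the text needs clarifying, but it is not an established error.

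**Conclusion.** The overall 0.05 stated in section 6.14.1 is not a property of the procedure as written. With the endpoint order kept in every branch, the procedure controls error at 5% within each dose and within each endpoint, and at no more than 10% across doses and endpoints. The worst case is 9.2% to 9.75%. With assumed effects of 0.547 the same pattern gives 5.9% to 8.8% at 100 per arm and 4.7% to 7.3% at 72. These figures rest on assumed endpoint correlations of 0 to 0.9, and the second set also on carrying 0.547 over to 400 mg and to CGI-I.

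Two stronger inferences are not supported. The primary comparison in section 6.13.1, taken alone, is a valid fixed sequence and is unaffected. And 9.75% is the error under one unfavourable pattern, not the rate to be expected. The point should be fixed because a stated error guarantee is wrong and correcting the text is cheap.

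**What to change.** Before unblinding:

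(a) Restate the claim in section 6.14.1: type I error is controlled at 0.05 within each dose across the primary and key secondary endpoints, and within each endpoint across doses, but not overall across doses and endpoints. Align the multiplicity statements in sections 6.12 and 6.13, or the plan will contradict itself.

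(b) Replace the sentence on no adjustment with an explicit rule: if only 400 mg wins the primary, CGI-I, Conners 3 and WFIRS-P are tested in that order for 400 mg at 0.05, stopping at the first non-rejection.

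Both are text changes. The overall claim is given up. No power is lost against the reading that keeps the order; against the looser reading, 400 mg loses its tests after a first failure in that branch.

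Only if the sponsor wants to keep an overall 0.05 must it choose between two options.

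*A single sequence*: primary, CGI-I, Conners 3, WFIRS-P, with 400 mg then 200 mg within each, stopping at the first non-rejection. Any 200 mg failure, including on the primary, then ends testing for 400 mg. Chance of a 400 mg claim on CGI-I / Conners 3 / WFIRS-P, with effect 0.547 assumed on every test:

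| Per arm, ρ | Section 6.14.1 rules | Single sequence |
|---|---|---|
| 72, 0 | 82 / 75 / 68% | 76 / 64 / 54% |
| 72, 0.7 | 86 / 82 / 80% | 80 / 74 / 69% |
| 100, 0 | 94 / 92 / 89% | 92 / 88 / 83% |
| 100, 0.7 | 95 / 94 / 93% | 93 / 90 / 88% |

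(At 72 per arm and ρ = 0, for CGI-I: 0.907² = 0.82 against 0.843 × 0.907 = 0.76.)

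*A prespecified alpha split* between the two dose chains, for example 0.025 each in every branch, with the endpoint order kept. Each dose's key secondary tests then run at the reduced level. If the family includes the primary, the 200 mg primary test pays too: its t-test power at 0.025 falls from 90% to 84% at 72 per arm, or from 97% to 95% at 100.

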6.14.1.1 Clinical Global Impression – Improvement (CGI-I)

The absolute value of CGI-I at week 8(EOS) will be analyzed using ANCOVA with treatment as a fixed classification variable and baseline CGI-S as a covariate. This ANCOVA analysis supersedes the ANOVA analysis described in the protocol. Each of the treatment groups (SPN-812 ER 200 mg and 400 mg) will be compared with the Placebo. The p-values, Least Squares means of the treatment groups, differences between the LS treatment means and placebo (SPN-812 ER 200 mg minus Placebo and SPN-812 ER 400 mg minus Placebo), 95% confidence intervals for the treatment differences will be computed. The summary of this analysis will be presented in Table 14.2.2.1.1 and listed in Listings 16.2.6.3.2- 16.2.6.5.

6.14.1.2 Conners 3-Parental Short Form

The Conners 3-PS will include 6 domains (subscales): inattention, hyperactivity/impulsivity, aggression, executive functioning, learning problems, and relationships.

The data for Conners 3-PS comprise derived T-scores for each domain rounded to the nearest integer. If a T-score ≤ 40 then the T-score will be set to 40 and if a T-score ≥ 90 then the T-score will be set to 90. If 1 of the subdomains is missing then the total score will be missing and the missing value will be handled using multiple imputation under MAR. A composite T-score will be calculated by averaging over the six domains (rounded to the nearest integer) and the change from baseline to Week 8 (EOS) in the composite T-score will be analyzed using ANCOVA model with fixed classification variable for treatment and baseline as a covariate. Each of the treatment groups

(SPN-812 ER 200 mg and 400 mg) will be compared with the Placebo. The p-values, Least Squares means, differences between the LS treatment means and placebo, and 95% confidence intervals for the treatment differences will be computed. The summary of this analysis will be presented in Table 14.2.2.1.2 and Listings 16.2.6.6, 16.2.6.7 and 16.2.6.8.

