6.6 Handling Missing Data

6.6.1 Missing Efficacy Variables

Missing items in ADHD-RS-5 scale

1. If more than 3 items of ADHD-RS-5 have missing or invalid data, the total score will be set to missing. If the total score is missing then both subscales (inattention or Hyperactivity/Impulsivity) will be set to missing.
2. If 3 items of ADHD-RS-5 or less have missing or invalid data, the values for the missing items will be imputed using the mean of the non-missing items rounded to the nearest integer.

With respect to the primary analysis, missing ADHD-RS-5 Total Scores will be assumed to be missing at random (MAR) (*See Panel on Handling Missing Data in Clinical Trials, (2010) National Research Council: The Prevention and Treatment of Missing Data in Clinical Trials*) that is, given the observed data, the reason for the missing data does not depend on the unseen data. The Mixed Model for Repeated Measures (MMRM) method, implemented via SAS® PROC MIXED (SAS/STAT Software), will be used for handling missing ADHD-RS-5 Total Scores under MAR assumption. The motivation behind MMRM is to solve the issue of addressing an on-treatment question, i.e. what happens if a typical subject completes their assigned treatment. MMRM does this by conditioning on the previous observations and other covariates that may inform on both missingness and outcome.

A sensitivity analysis will be performed by assuming missing ADHD-RS-5 Total Scores are not missing at random (MNAR) ([Yang, 2014](#)), that is, the probability that an observation is missing may depend on its underlying unobserved value. This will be implemented using SAS® PROC MI and SAS® PROC MIANALYZE (SAS/STAT Software).

For secondary endpoints, missing values will be assumed as missing at random (MAR). Missing data will be imputed using SAS® PROC MI (SAS/STAT Software).

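### A Week 8 Conners 3 form with one missing domain is re-imputed from treatment and baseline alone, so the observed domains do not inform the composite analysis

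*SAP*

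**What the plan says.** SAP Section 6.14.1.2 builds the parent-form endpoint from six domain T-scores: "A composite T-score will be calculated by averaging over the six domains (rounded to the nearest integer"). Each domain is bounded: "If a T-score ≤ 40 then the T-score will be set to 40 and if a T-score ≥ 90" it is set to 90. For incomplete forms, with MAR assumed, the rule is "If 1 of the subdomains is missing then the total score will be missing and the missing value will be handled using multiple imputation".

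Section 6.14 says how that imputation runs: "All secondary analyses are based on the ITT population with missing values imputed at week 8 (WK8) using multiple imputation (MI) assuming MAR". Its code lists "VAR TREATMENT BASELINE WK8(EOS") as the only variables. No other section gives a separate model for Conners 3.

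Section 6.14.1 puts the endpoint second in the key secondary order: "sequentially ordered endpoints for testing: 1) CGI-I, 2) Conners-3, 3) WFIRS-P". A dose goes forward to WFIRS-P only if it was retained on Conners 3. Section 6.14.2.4 repeats the parent-form analysis for the self-report, which has five domains (Section 4).

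**The concern.** The value declared missing in Section 6.14.1.2 is the composite, and the model in Section 6.14 takes one baseline and one Week 8 variable per endpoint. Read together, they turn a form that is five-sixths observed into one treated as wholly missing. The replacement is drawn without sight of the five scores recorded for that child at that visit.

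Two things are at stake for the second key secondary test. One is precision: an affected child contributes no Week 8 information. The other is the plausibility of MAR. If the absence of a domain is related to how the child scored on the other domains at Week 8, the data are missing at random given what was collected, but not given what the model uses.

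**Working it through.** **The plan's own figure.** Section 3.5 gives 72 per group for 90% power at effect size 0.547, two-sided 5%. The noncentral t distribution gives 90.3% at 72 per group and 89.9% at 71, so the figure reproduces. 72/(1 − 0.279) = 99.9, hence 100 randomised per group. The point does not depend on these numbers; they serve only as a yardstick below.

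**Assumed inputs (not in the SAP).** Equal domain variances; a common inter-domain correlation ρ of 0.3 to 0.7; a correlation r of 0.3 to 0.7 between baseline and Week 8 composites; a share f of children with exactly one Week 8 domain missing of 2%, 5% or 10%.

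**1. What the five observed domains carry.** With unit domain variance, Var(six-domain mean) = (1 + 5ρ)/6 and Var(five-domain mean) = (1 + 4ρ)/5. Their covariance is (1 + 5ρ)/6. So R² = [(1 + 5ρ)/6] / [(1 + 4ρ)/5]:
- ρ = 0.3: 0.4167/0.4400 = 0.947
- ρ = 0.5: 0.5833/0.6000 = 0.972
- ρ = 0.7: 0.7500/0.7600 = 0.987

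For the self-report, four of five domains give [(1 + 4ρ)/5] / [(1 + 3ρ)/4]: 0.440/0.475 = 0.926 at ρ = 0.3 and 0.760/0.775 = 0.981 at ρ = 0.7.

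**2. What the imputation model uses instead.** Within arm, the baseline composite explains r²: 9%, 25% or 49% at r = 0.3, 0.5 or 0.7.

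**3. A bound that needs no correlation.** Domain T-scores lie between 40 and 90. Five observed domains therefore fix the composite to within (90 − 40)/6 = 8.3 points before rounding. The planned draw ignores that band.

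**4. Standard error under the SAP rule.** Imputing an outcome from the covariates already in the ANCOVA adds no information, so the standard error grows by 1/√(1 − f) − 1:
- f = 2%: 1/√0.98 − 1 = 1.0%
- f = 5%: 1/√0.95 − 1 = 2.6%
- f = 10%: 1/√0.90 − 1 = 5.4%

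**5. Standard error if the observed domains are used.** The information lost per affected child falls to about (1 − R²)/(1 − r²) of the ANCOVA residual variance. At f = 10% and ρ = 0.3, this is 0.053/0.75 = 0.071 for r = 0.5, a rise of 1/√(1 − 0.0071) − 1 = 0.4%. In the least favourable corner, r = 0.7, it is 0.053/0.51 = 0.104, a rise of 0.5%.

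**6. Simulation check.** 1,500 replicates; two arms of 100; domain SD 12; true difference −5; ρ = 0.5; correlation 0.5 between the common factors at the two visits, which makes r = 0.25/0.583 = 0.43. At f = 10% the standard error was 1.195 with full data, 1.263 under the SAP rule (+5.7%) and 1.200 with the mean of the five observed domains (+0.4%).

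**7. If missingness follows the observed Week 8 domains in the active arm only.** In the same set-up, with worse scores more likely to be incomplete, the SAP rule moved the estimate away from the full-data result by −0.09, −0.22 and −0.47 points at f = 2%, 5% and 10%. The five-domain mean moved it by less than 0.02.

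**8. Yardstick for power.** On the design of Section 3.5, replacing 72 by 72(1 − f) takes power from 90.3% to 89.7%, 88.8% and 87.1%. The effect size there belongs to the ADHD-RS total, not to Conners 3, so this shows scale only.

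**The case against.** The best defence is that the rule is prespecified, clear and the same in every arm. If missingness depends only on treatment and baseline, it gives an unbiased result that is merely less precise. That stands: the bias in step 7 needs a mechanism that nothing in the SAP suggests.

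Nor is it shown how often the rule would apply. Domain T-scores enter the analysis already derived, and the SAP does not say how missing items are handled in that scoring. The 2% to 10% range is an assumption, and the true rate may be near zero.

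A reader might infer that the SAP contradicts its own practice, because for ADHD-RS-5 it says "If 3 items of ADHD-RS-5 or less have missing or invalid data, the values for the missing items will be imputed" from the child's other items. The documents do not support this. That rule concerns up to 3 scattered items. A whole ADHD-RS-5 subscale is 9 items, so losing one sets the total and both subscales to missing. PSI-4-SF scores likewise need no more than one missing item in any subscale. Only WFIRS-P, an average over answered items, is more lenient.

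A reader might also infer that five domain scores are discarded outright. They remain defined variables in Section 4 and are lost only to the composite analysis.

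Finally, the description is exact only for a domain missing at Week 8. For one missing at baseline, the text of Section 6.14 speaks of imputing Week 8 while its code would also fill the baseline value, and the SAP does not settle which applies.

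**Conclusion.** The point holds as one of efficiency and of how plausible MAR is, not of validity. For an affected Week 8 parent form, the plan replaces scores that explain about 95% to 99% of the composite's variance with a draw from treatment and a baseline that explains 9% to 49%, under the assumed correlations. Over the whole comparison, the standard error rises by about 1.0%, 2.6% or 5.4% at an assumed 2%, 5% or 10% of children with a single missing domain, against about 0.5% or less if the observed domains are used. The SAP gives no such rate; if these forms are rare, the effect on the second key secondary test is small. This is a worthwhile improvement of low urgency. It does not support a claim that the test is biased or that the plan is inconsistent with its own scoring rules.

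**What to change.** In Sections 6.14.1.2 and 6.14.2.4, replace composite-level imputation by domain-level imputation under MAR. Include treatment with all baseline and Week 8 domain T-scores (12 scores for the parent form, 10 for the self-report), apply the 40 to 90 limits to imputed domains, and average the domains within each imputed dataset before the ANCOVA. Say that this also covers two or more missing domains and a domain missing at baseline. Forms missing entirely are then still fully imputed, and partial forms keep what was observed.

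The cost is SAP wording and a separate PROC MI call with a longer variable list. No new data are needed, and the endpoint and test are unchanged. The downside is a larger imputation model on bounded scores: normal-regression draws for domains near 40 or 90 will be clipped, including for wholly missing forms. With about 300 children the parent-form model is manageable; the self-report model rests on fewer, since only ages 8 to 11 complete it.
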